1.0 Objectives

Specific Aim 1. Implement CtP for 20 family members of persons with ADRD in four RHS regions (Phase I). A convergent parallel mixed methods design (quan + QUAL) will be implemented to examine the feasibility, acceptability, and utility of CtP over a 1-month period. Twenty caregivers from four RHS regions who use CtP will be interviewed at 1-month to obtain information and guidance on how CtP is best administered in this service context. Three RHS interventionists will also be interviewed after phase I participants complete CtP. The combination of quantitative and qualitative data from Phase I will offer robust data to refine and further prepare CtP for subsequent evaluation in Phase II.

Specific Aim 2. Evaluate the preliminary efficacy and implementation of CtP (Phase II). By utilizing an embedded randomized controlled evaluation, the second phase of this project will implement the findings of Aim 1 to evaluate CtP. A newly enrolled sample of 100 ADRD caregivers will be randomly assigned to one of two groups: one that receives the CtP with guidance from caregiver support staff and a usual care control. Three- and six-month outcomes will include caregiver self-efficacy and distress; caregiver use of recommended support; and service utilization on the part of persons with ADRD. These findings will provide initial insights into efficacy of CtP as well as the acceptability and utility of CtP over time. The results will also serve as a source of empirical estimates to inform subsequent larger-scale evaluation and translation efforts.

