3.0 Study Endpoints/Events/Outcomes

- 3.1 Primary Endpoint/Event/Outcome: Caregiver self-efficacy
- 3.2 Secondary Endpoint(s)/Event(s)/Outcome(s): Caregiver distress (role captivity, role overload, loss of intimate exchange, depressive symptoms); Use of CtP-recommended services

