Note: If desired, the telephone-based surveys may be administered in hard copy. For Phase I, staff will call participants 1 month (+/- 7 days) following baseline completion to complete their follow-up survey, or mail their follow up survey at that time if requested. Several telephone reminders will be provided as needed to facilitate completion. Completion of this follow-up may occur outside of the timeframe for initial contact. Phase II follow-up will include a disposition form as well, and follow these same procedures, with staff attempting to contact participants via phone or mailing surveys 3 and 6 months (+/- 7 days) from completion of the baseline survey. For those opting for mail survey completion, staff may obtain the disposition status prior to mailing the appropriate survey within 7 days of obtaining this information. Staff may send a hard copy survey (omitting the disposition form as needed) if unable to reach them via phone, in an attempt to reduce loss to follow up. Those selected for the final telephone interview in Phase II will be contacted within 3 months of completion of their final 6 month survey (however, completion of the interview may occur outside of this timeframe based on participant scheduling needs). Three or 6 month follow-up surveys conducted via phone are conducted by a blinded staff member.

The UMN team will also determine the degree to which participants use and apply CtP recommendations. The research assistant or research coordinator will conduct a brief semi-structured telephone interview 1 month following baseline. If the participant has not completed CtP by the 1 month time-point, the participant will be considered lost to follow up, and the checklist and interview will not be administered. The research assistant or coordinator will also administer semi-structured interviews to the three CtP interventionists to obtain their perceptions when administering the tool to ADRD caregivers. These interviews will be conducted after the Phase I participants have completed CtP. The open-ended responses will provide in-depth information on facilitators to use and barriers to refine prior to Phase II. Recorded interviews will be transcribed (by Production Transcripts) for data analysis.

Phase II Procedure

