17.0 Data Management

17.1 Data Analysis Plan:

Phase I quantitative analyses: Specific Aim 1. As the Phase I aim is to examine the feasibility, acceptability, and utility of CtP within the partnering RHS sites, the quantitative analyses of the R21 phase will largely rely on descriptive statistics. Specifically, Phase I quantitative analyses will utilize frequency tables and means to examine sample characteristics and item-level responses to the CtP review checklist.

Phase II quantitative analyses: Specific Aim 2. Logistic regression analyses will determine whether participation in the CtP treatment group results in utilization of caregiver support programs over the 6-month evaluation period when compared to ADRD caregivers in the control group. Care to Plan treatment vs. control group membership will be the independent variable of interest; caregiver use of CtP recommended services will serve as the dependent variables.

Additional variables will serve as covariates, including time-invariant and time-varying measurements of stress process covariates. Odds ratios will be examined in order to determine the degree to which these variables explain the observed effects of CtP on dependent variable occurrence. Data available at baseline, 3 months, and 6 months will allow for descriptive and growth curve analyses of rate of change in key outcomes: caregiver efficacy and caregiver distress.^{16,17} The individual growth curve model conceives of development, or change, as the function of an individual growth curve plus random error. In our outcome evaluations, the baseline value will be included as a covariate and time will be “centered” at 6-months post-baseline. We will specifically examine whether individual growth parameter estimates have significant variance around the

PROTOCOL TITLE: Care to Plan: Preliminary Efficacy of a Tailored Resource for Family Members of Persons with Dementia

mean trajectories of change in key dependent variables, and then determine whether treatment group assignment influences outcome change parameters in these models. IBM SPSS 21 will be utilized to conduct the within-subject growth curves; the PI has extensive experience conducting growth curve/trajectory analyses.¹⁸⁻²⁴ An additional advantage of this approach is its ability to incorporate missing longitudinal data points, given assumptions of missing at random.²⁵

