17.2 Power Analysis

Longitudinal analysis procedures (growth curve modeling) will be utilized to capitalize on the randomized design and the multiple waves of data that will be collected. The objective of the Phase II analyses is to generate power estimates for a subsequent, larger scale evaluation of CtP. However, a sample size of 100,

PROTOCOL TITLE: Care to Plan: Preliminary Efficacy of a Tailored Resource for Family Members of Persons with Dementia

factoring in a conservative 10% attrition rate at 6 months, would have sufficient power to detect a medium/large effect size).^{30,31} As noted in various recommendations, a sample of 20 is considered adequate for semi-structured interview protocols to ensure the richness of open-ended data collected.^{32,33}

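### The planned test of variance in individual change cannot be relied on, whether baseline is both a growth-curve wave and a covariate or a covariate only

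*Combined protocol and SAP*

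**What the plan says.** Section 17.1 introduces the longitudinal analysis of self-efficacy and distress with "Data available at baseline, 3 months, and 6 months will allow for descriptive and growth curve analyses of rate of change in key outcomes". In the same paragraph it adds "In our outcome evaluations, the baseline value will be included as a covariate and time will be" centred at 6 months after baseline. Nothing there says that the baseline wave leaves the outcome vector once it becomes a covariate.

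The next sentence gives two steps in order: "We will specifically examine whether individual growth parameter estimates have significant variance around the" "mean trajectories of change in key dependent variables, and then determine whether treatment group assignment influences outcome change parameters in these models". The covariance of the random effects is not given, and no treatment coefficient is named.

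Other sections do not settle this. Section 3.1 has "Primary Endpoint/Event/Outcome: Caregiver self-efficacy" without a time point. Specific Aim 2 in section 1.0 says "Three- and six-month outcomes will include caregiver self-efficacy and distress". On timing, section 5.1 has staff phoning or "mailing surveys 3 and 6 months (+/- 7 days) from completion of the baseline survey".

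**The concern.** A growth curve can use baseline as its first outcome, or an analysis of later outcomes can adjust for baseline. Doing both in one model regresses the baseline outcome on itself. Its residual then shrinks towards zero while the later residuals do not, and a random slope can absorb that artificial widening as though people were changing at different rates. If baseline is only a covariate, two outcome waves remain, which is too few to separate a random slope from a random intercept and residual error.

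The variance test is a stated step for the primary outcome and for distress. As written, its answer could reflect the coding and not the caregivers. Section 17.2 also says "The objective of the Phase II analyses is to generate power estimates for a subsequent, larger scale evaluation of CtP", so an inflated slope variance would be a poor planning input if it were carried forward.

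**Working it through.** **Inputs.** From the plan: waves at 0, 3 and 6 months and centring at 6 months (section 17.1); 1:1 allocation (section 5.1); 100 enrolled with 10% attrition (section 17.2), so 100 × 0.9 = 90, or 45 per arm. Not in the plan, so assumed: SD 1, equal wave correlation ρ of 0.3 to 0.7, two-sided 0.05, complete data, time unit 3 months (times -2, -1, 0). The plan gives no figure for the variance test to reproduce. The main simulation used REML with 2,000 runs per scenario (Monte Carlo SE at most 1.1 points) and a likelihood-ratio test (LRT) against 5.99.

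**1. Baseline as wave and covariate, random intercept and slope freely correlated.** With one covariate coefficient b, the residual variance is (1 - b)² at baseline and 1 + b² - 2bρ later. At ρ = 0.5 the fitted b averaged 0.794:
- baseline: (1 - 0.794)² = 0.042
- 3 and 6 months: 1 + 0.630 - 0.794 = 0.836, about 20 times larger.

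Results with true slope variance zero:

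| Correlation | 0.3 | 0.4 | 0.5 | 0.6 | 0.7 |
|---|---|---|---|---|---|
| LRT significant, both roles | 99.6% | 99.9% | 100% | 100% | 100% |
| Median LRT, both roles | 31.4 | 36.3 | 41.6 | 46.2 | 50.3 |
| Mean slope variance, both roles | 0.205 | 0.181 | 0.156 | 0.129 | 0.099 |
| LRT significant, three waves, no covariate | 2.1% | 3.5% | 3.2% | 3.5% | 3.5% |

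A second simulation (300 runs each, LRT against a 50:50 mixture of chi-square on 1 and 2 df) gave 99.7%, 99.7% and 100% at ρ = 0.3, 0.5 and 0.7, against 3.7%, 4.0% and 4.0% without the covariate. Adding a baseline-by-time term did not help (99.7-100%).

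With true slope variance 0.05 and 0.10 (intercept variance 0.6, residual 0.4), the estimates were 0.179 and 0.231 with the covariate, and 0.054 and 0.102 without it. The inflation is 0.179/0.05 = 3.6 and 0.231/0.10 = 2.3 times.

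**2. Baseline as covariate only.** Write τ0 and τ1 for the intercept and slope variances, c for their covariance and σ² for the residual variance. With outcomes at t = -1 and 0:
- V6 = τ0 + σ²
- V3 = τ0 - 2c + τ1 + σ²
- Cov(3,6) = τ0 - c

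That is three moments for four parameters (Jacobian rank 3). Variation in actual visit times adds a little information. Expected-information standard errors (SE) of τ1, n = 90:

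| Correlation | 0.4 | 0.5 | 0.7 |
|---|---|---|---|
| Two waves, visits within ±7 days | 1.26 | 1.06 | 0.65 |
| Same, plus late completion averaging 21 days (assumed) | 0.22 | 0.19 | 0.12 |
| Three waves, no covariate | 0.063 | 0.053 | 0.032 |

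Even in the most favourable two-wave case, a true variance of 0.10 is only 0.10/0.12 = 0.83 standard errors.

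**3. A separate trap: uncorrelated random effects centred at 6 months.** Setting c = 0 in step 2 gives τ1 = V3 - V6, so real divergence (V6 above V3) is estimated as zero. With three waves, the variance τ0 + t²τ1 + σ² is likewise forced to be smallest at 6 months. Share significant for true slope variance 0.05 and 0.10:
- both roles: 0% and 0%
- covariate only: 0.3% and 0.0%
- three waves, no covariate: 2-4% in two sets of runs, with estimates of about 0.01
- three waves, no covariate, freely correlated: 24.5% and 66.2%.

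**4. Treatment test, no true effect.** Type I error of the 6-month term:
- covariate only: 4.2-5.3% (6.0% and 7.0% when change truly varies)
- both roles, unstructured random slope: 3.4-5.3%, and 6.0-6.3% in the smaller simulations of 300-400 runs
- both roles, random intercept only: 12.4-14.2%.

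Treatment-by-time with both roles and an unstructured random slope: 1.8-3.5%.

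**The case against.** The strongest reply is that the double role is inferred. Listing three time points as available data does not by itself put baseline in the outcome vector, and the wording of Specific Aim 2 favours baseline as covariate only. This stands as far as it goes: the plan does not say which role is meant. It does not rescue the test, because on that reading the slope variance is not usefully identified. The failure is then an uninformative test and not a misleading one.

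It is also fair that the ±7 days governs when staff make contact, and that section 5.1 lets surveys be finished later. Quoting only the SE of 0.65-1.26 would overstate the weakness; 0.12-0.22 is the counterpart under the assumed 21-day delay.

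A reader might infer from step 3 that the double role also makes the test blind to real variation. It does not. That blindness comes from forcing zero covariance at this centring, it appears without the baseline covariate too, and the plan does not state that structure.

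Finally, the variance test is an ancillary step. The plan puts it before the treatment test in order but does not make the treatment test conditional on it.

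**Conclusion.** The concern holds for the test of variance in individual change. With baseline in both roles and freely correlated random effects, the test is significant in about 100% of trials with no slope variance, and true values of 0.05 and 0.10 are overestimated by about 3.6 and 2.3 times. With baseline as covariate only, it is uninformative. The SD, alpha, complete data and time unit are assumptions, but the false-positive result is stable across correlations 0.3 to 0.7.

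Two stronger conclusions are not supported. First, the randomised comparison is not shown to be invalid: the 6-month term is near nominal with baseline as covariate only, and with both roles plus an unstructured random slope. The inflated case needs both roles with a random intercept only, which the plan does not specify. Second, section 17.2 does not say that the slope variance will feed the later trial's power calculation, so that harm is conditional. The unnamed treatment coefficient is mainly missing detail.

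**What to change.** In section 17.1:

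- Give baseline one role in each model.
- Run any test of variance in change only in the three-wave model without the baseline covariate, with an unstructured (freely correlated) random intercept and slope. Merely stating the covariance is not enough, because an uncorrelated structure at this centring would hide true variation.
- Report the slope variance with its interval, and do not make the treatment test depend on it.
- For the treatment effect, use 3 and 6 months as outcomes with baseline as covariate, or three waves without that covariate. State which coefficient is primary; the CtP-minus-control difference at 6 months fits the stated centring.

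The choice of coefficient matters. For a 0.6 SD effect reached by 3 months and kept (correlation 0.4), the covariate-only model has 86.8% power for the 6-month term and 4.8% for the slope.

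The cost is a few lines of wording and code, with no new data. The valid variance test has limited power here, about 25% and 66% for true slope variance 0.05 and 0.10. If the three-wave option keeps linear time, a kept effect of 0.60 is fitted at 6 months as 0.60 × (2/3 + 1/2) = 0.70; categorical visits would avoid this.

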17.2 Power Analysis

Longitudinal analysis procedures (growth curve modeling) will be utilized to capitalize on the randomized design and the multiple waves of data that will be collected. The objective of the Phase II analyses is to generate power estimates for a subsequent, larger scale evaluation of CtP. However, a sample size of 100,

PROTOCOL TITLE: Care to Plan: Preliminary Efficacy of a Tailored Resource for Family Members of Persons with Dementia

factoring in a conservative 10% attrition rate at 6 months, would have sufficient power to detect a medium/large effect size).^{30,31} As noted in various recommendations, a sample of 20 is considered adequate for semi-structured interview protocols to ensure the richness of open-ended data collected.^{32,33}

17.3 Data Integrity

Regular Zoom conference meetings that include [name], [name] and the RHS and UMN teams will take place to ensure study rigor/integrity and progress. [name] is currently utilizing a similar strategy on a national translational project where he and the other PI are located at different institutions (R01 AG049692). Combined with annual in-person meetings (as COVID-19 safety restrictions allow) between [name] and [name] at the Gerontological Society of America and in Williamsburg, VA, the project management plan will facilitate coordination between the University of Minnesota and RHS.

18.0 Confidentiality

18.1 Data Security: Please see above. No consent form will be placed in participants' medical, employment, or educational records.

Please note: [If there is interest in Care to Plan, the Riverside staff would complete the permission for contact form and securely share the contact information with the UMN research team]. Riverside Senior Care Navigators or other RHS staff may communicate/document about referrals made to Riverside Senior Care Navigation for consultation, interest/involvement in the Care to Plan study, and other referrals provided to individuals who may be enrolled in the Care to Plan study. This communication/documentation occurs outside of the study context (as a part of their routine roles in care consultation with Riverside Health System), and UMN study staff do not have access to the Riverside Epic electronic health record or to the staff's internal time tracking system where staff reference this information (SalesForce/Livwell).

19.0 Provisions to Monitor the Data to Ensure the Safety of Participants

18.1 PARTICPANTS SAFETY

18.1.1 Potential Risks and Benefits for Participants

Potential Risks: Since the study involves no invasive procedures, there will be no physical risks to study participants. The consideration of need is potentially stressful, and thus there are possible psychological risks for the caregiver. However, the research team has considerable experience providing psychosocial support to dementia caregivers on various protocols and serious psychological risks are unlikely to occur based on this experience. The potential social or legal risks for the participants relate

PROTOCOL TITLE: Care to Plan: Preliminary Efficacy of a Tailored Resource for Family Members of Persons with Dementia

only to possible violations of confidentiality. Given the procedures outlined below, such risks are highly unlikely.

Potential Benefits: We believe participation in both Phase I and Phase II will yield benefits for participants. Utilization of CtP will provide dementia caregivers with improved ability to identify supportive services that are tailored to their needs. Caregivers will be paid up to \$100 following their participation in the study.

18.1.2 Adverse Event and Serious Adverse Event Collection and Reporting

In addition to ongoing monitoring of protocol and human subjects compliance, [name] and research team will generate safety reports annually that will list adverse events, serious events, unexpected events, events related to or associated with the intervention, and the potential causality of the intervention to the event for each participant if they occur. If the research team becomes aware of an adverse event or unanticipated problem occurring while a participant is enrolled in the study (consent through the participant's final data collection), the event will be documented and/or reported per the protocol below. Conditions existing prior to study enrollment that have not worsened/changed will not be considered adverse events and will not be documented/reported. Per the University of Minnesota IRB guidelines, all events or information that indicates a new or increased risk, or a safety issue, will be promptly reported.

Taken directly from the NIA Adverse Event and Serious Adverse Event Guidelines, the definition of each event is as follows:

Adverse event (AE). Any untoward or unfavorable medical occurrence in a human study participant, including any abnormal sign (e.g. abnormal physical exam or laboratory finding), symptom, or disease, temporally associated with the participants' involvement in the research, whether or not considered related to participation in the research.

Serious adverse event (SAE). Any adverse event that results in death; is life threatening, or places the participant at immediate risk of death from the event as it occurred; requires or prolongs hospitalization; causes persistent or significant disability or incapacity; results in congenital anomalies or birth defects; and/or is another condition which investigators judge to represent significant hazards.

Unanticipated problem (UP). any incident, experience, or outcome that meets all of the following criteria: unexpected, in terms of nature, severity, or frequency, given (a) the research procedures that are described in the protocol-related documents, such as the IRB-approved research protocol and informed consent document; and (b) the characteristics of the study population; related or possibly related to participation in the research (in this guidance document, possibly related means there is a reasonable possibility that the incident, experience, or outcome may have been caused by the procedures involved in the research);

PROTOCOL TITLE: Care to Plan: Preliminary Efficacy of a Tailored Resource for Family Members of Persons with Dementia

and suggests that the research places participants or others at a greater risk of harm (including physical, psychological, economic, or social harm) than was previously known or recognized.

Phase II participants will be asked at 3 and 6 month follow up: “In the last three months, since your last survey, was there any new or worsening health problem that caused you to be unable to perform your daily routine (i.e. not go to work or volunteer), seek medical care (i.e. go see your doctor, go to the ER or hospital), or take a new medication?” Those medical events will be documented as adverse events. Other events that will also be considered adverse events are included below.

All AEs (following consent) will be collected on an adverse event form, in electronic format. AEs experienced by a participant during a study procedure (i.e. intervention/survey) will be reported within 5 days of discovery to the University of Minnesota IRB (per the University’s IRB procedures) and annually to the NIA in data monitoring reports.

AE that occur outside of the context of a study procedure (i.e. intervention/survey), as well as those that are determined to be not related to the participant’s involvement in the study, will be documented via the team’s electronic AE form and included in the annual report (to be shared with IRB, Safety Officer, and NIA Program Officer).

SAEs occur that are unanticipated (i.e. not listed in the Data and Safety Monitoring Plan) and related to the intervention will be reported to the IRB, NIA Program Officer, and to the Safety Officer within 48 hours of our team’s knowledge of SAE. The summary of all other SAEs (i.e. those determined not related to study involvement) will be included in the annual report (to be shared with IRB, Safety Officer, and NIA Program Officer).

Deaths determined not-related to the study will be reported to the IRB within 5 days of the team’s knowledge of the participant’s death, and reported to the Safety Officer and NIA Program Officer via routine annual reports. Though unlikely, if a participant’s death during the project enrollment has a possible relationship to the study, it will be reported in expedited fashion (within 24 hours of the team’s knowledge of a participant’s death) to the University of Minnesota IRB, the NIA Program Officer, and to the Safety Officer. A written SAE report will be submitted soon thereafter.

No adverse events are expected to be related to study involvement. However, due to the nature of our study population, possible adverse events (i.e. general medical events and/or emergencies) may occur during the time a participant is enrolled in the study. These events will be documented and/or reported according to the protocol.

PROTOCOL TITLE: Care to Plan: Preliminary Efficacy of a Tailored Resource for Family Members of Persons with Dementia

Due to the nature of our study population, the following scenarios may be encountered during project enrollment, and will be handled per the below protocol.

- Considered adverse events:
 - Medical events or emergencies: Research staff will call 911 as needed for emergencies (if during study procedure) or provide psychological support and encourage the participant to follow-up with their medical provider as needed (if occurred outside of study procedures). These medical issues (unrelated to study involvement) are considered expected, due to the nature of our study population. These events will be documented/reported as adverse events per above protocol if they meet one of the following criteria: a new or worsening health problem that causes the participant to 1) be unable to perform their daily routine, 2) seek medical care (provider visit, hospitalization, residential care placement, etc.), or 3) take a new medication. *[Note: Medical events or emergencies of a non-participant will not be considered/document as adverse events].*
 - Death of participant is reported promptly to the University of Minnesota IRB per above procedures (and is also reported to the Safety Officer and NIA within 24 hours of the team's knowledge if determined potentially related to study involvement; otherwise is included on routine annual reports shared with Safety Officer and NIA). Deaths in our study population (unrelated to study involvement), are considered expected. *[Note: Deaths of a non-participant will not be considered/document as adverse events].*
 - Suicidal ideation of participant: If participant informs study staff of thoughts of suicide, staff will discuss the concern with the participant and offer resources (i.e. [name] line, healthcare provider, etc.). Staff will ask them to provide verbal agreement not to harm themselves, and alert PI immediately. If necessary, staff will call 911. This will be documented/reported as serious adverse event.
 - Abuse/Neglect of participant: Document as adverse event per above protocol. If indicated, make vulnerable adult report to adult protective services.
 - Other events that in the discretion of the PI should be reported as adverse events.
- Not considered adverse events:

PROTOCOL TITLE: Care to Plan: Preliminary Efficacy of a Tailored Resource for Family Members of Persons with Dementia

- If a participant scores 16 or higher on the CES-D [risk for depression], study staff will provide resources as needed (i.e. <https://www.samhsa.gov/>, healthcare provider, and Riverside/Senior Care Navigation). Mental health concerns are common in our study population and fluctuation of assessment scores is expected. Unless participant indicates a concern regarding self-harm or that the health issue has caused them to: be unable to perform their daily routine, seek medical care, or take a new medication, it will not be documented as an adverse event.
- Survey responses indicating changes in sleep, stress/anxiety, activities of daily living, or general well-being alone will not trigger an adverse event report. These concerns are common in our study population and fluctuation of assessment scores is expected. Unless participant indicates a concern regarding self-harm or that the health issue has caused them to: be unable to perform their daily routine, seek medical care, or take a new medication, it will not be documented as an adverse event.
- Routine or planned medical encounters for symptoms or conditions that are not new, worsened, or changed since enrollment, as well as those events that have not caused the participant to: be unable to perform their daily routine, seek medical care, or take a new medication, will not be documented as an adverse event.
- A physical attack or injury to participant by a non-participant (i.e. care recipient) would be documented/reported as an adverse event if the participant requires medical care. *[Note: Other potential dementia related behaviors that do not result in participant injury are not considered adverse events.]*
- Participant reports that non-participant (i.e. care recipient or person with memory impairment) displays risk-behavior (i.e. aggression/threats, comments about death or self-harm): This will not be documented as adverse event, as individual is not enrolled in the study. If participant reports concern to study staff, study staff will encourage them to follow up with healthcare provider or Riverside/Senior Care Navigation for resources.
- Suicidal ideation of non-participant (care recipient): If participant shares concern about care recipient (non-participant) suicidal ideation, study staff will talk about the concern and provide resources as requested (i.e. [name] line, healthcare provider, etc.). This is not documented as an adverse event, as individual is not enrolled in the study.

PROTOCOL TITLE: Care to Plan: Preliminary Efficacy of a Tailored Resource for Family Members of Persons with Dementia

- Abuse/Neglect of non-participant: Document and report as an adverse event only if study participant is involved. Make vulnerable adult report to adult protective services as indicated.
- Driving with dementia/cognitive impairment (participant or non-participant): Provide resources as needed (i.e. <https://alz.org/help-support/caregiving/safety/dementia-driving>, <https://www.thehartford.com/resources/mature-market-excellence/dementia-driving>, etc.), encourage family involvement with medical provider, and adhere to local laws. This is not considered/document as an adverse event.
- Unlicensed driving (participant or non-participant): If study staff are informed that an individual is driving without a license, staff will encourage driving in accordance with local laws and explain potential consequences. This is not considered/document as an adverse event.
- Environmental/home hazards (i.e. unlocked/loaded weapons, other safety concerns): Encourage remedying this situation for safety; recommend in-home safety assessment as needed. This is not considered/document as an adverse event unless immediate risk of harm is identified (i.e. abuse/neglect).

As taken directly from the NIA Adverse Event and Serious Adverse Event Guidelines, the severity, expectedness, and relatedness of each AE and serious adverse event (SAE) will be graded as follows:

Severity

- **Mild**: Awareness of signs or symptoms, but easily tolerated and are of minor irritant type causing no loss of time from normal activities. Symptoms do not require therapy or a medical evaluation; signs and symptoms are transient.
- **Moderate**: Events introduce a low level of inconvenience or concern to the participant and may interfere with daily activities, but are usually improved by simple therapeutic measures; moderate experiences may cause some interference with functioning
- **Severe**: Events interrupt the participant's normal daily activities and generally require systemic drug therapy or other treatment; they are usually incapacitating

Expectedness

- **Unexpected** - nature or severity of the event is not consistent with information about the condition under study or intervention in the protocol, consent form, product brochure, or investigator brochure.
- **Expected** - event is known to be associated with the intervention or condition under study.

Relatedness

The potential event relationship to the study intervention and/or participation is assessed by the site investigator. A comprehensive scale in common use to categorize an event is:

- ***Definitely Related***: The adverse event is clearly related to the investigational agent/procedure – i.e. an event that follows a reasonable temporal sequence from administration of the study intervention, follows a known or expected response pattern to the suspected intervention, that is confirmed by improvement on stopping and reappearance of the event on repeated exposure and that could not be reasonably explained by the known characteristics of the subject's clinical state.
- ***Possibly Related***: An adverse event that follows a reasonable temporal sequence from administration of the study intervention follows a known or expected response pattern to the suspected intervention, but that could readily have been produced by a number of other factors.
- ***Not Related***: The adverse event is clearly not related to the investigational agent/procedure - i.e. another cause of the event is most plausible; and/or a clinically plausible temporal sequence is inconsistent with the onset of the event and the study intervention and/or a causal relationship is considered biologically implausible.

